9.3.2. Withdrawal Procedures

- If it is necessary for a subject to discontinue the study drug/study earlier than planned, subjects should complete Early Termination procedures (see Section 13.13) and return the study drug, as applicable. Date of last dose should be recorded.
- The Investigator must notify the Sponsor and the Medical Monitor within 24 hours when a subject has been withdrawn from the study. Any subject withdrawn because of a related AE (whether serious or non-serious), including clinically significant abnormal laboratory test values, will be evaluated by the Investigator or a designee and be treated and/or followed until the symptoms resolve or values return to normal or acceptable levels, as judged by the Investigator.
- If a subject does not return for a scheduled visit, every effort should be made to contact the subject. If a subject withdraws from the study, the Investigator or designee should inquire about the reason for withdrawal, and follow-up with the subject by phone as scheduled to collect AE information.
- If the subject withdraws from the study and also withdraws consent for disclosure of future information, no further evaluations will be performed, and no additional data will be collected. The Sponsor may retain and continue to use any data collected before such withdrawal of consent; these data will be included in the safety database.

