	12. History, within the last 2 years, of alcohol abuse, significant mental illness, or physical opioid dependence
Food Journal requirement	While on study drug, subjects are recommended to avoid eating foods high in PUFAs. Subjects will keep food journals from screening through the completion of month 1 on study drug. After month 1, subjects will keep 2-week food journals prior to next scheduled onsite visit. Subjects (or parents/caregivers, as applicable) will have an initial call and as needed with the diet coach to discuss food journal completion requirements.
Prohibited Medications	Supplements that contain EPA or DHA are prohibited. Oil-based supplements like Fish oil, Cod Liver oil, Edible algae oil and Flax oil are also prohibited.
Statistical methods	Demographic data will be presented using descriptive statistics (e.g., mean, standard deviation, median, and range). Exposure to study drug and reasons for discontinuation will be tabulated. Safety variables will be tabulated and presented for all subjects who receive study drug or placebo capsules. Adverse events will be coded using the Medical Dictionary for Regulatory Activities (MedDRA). The incidence of treatment-emergent AEs will be presented by system organ class and preferred term. Adverse events will be presented by severity and relationship to

study drug. Changes from Baseline in clinical laboratory parameters and vital signs will be summarized across time. Shift tables will be provided for selected laboratory parameters. Physical examination results will be presented in listings.

Change from baseline (CFB) will be analyzed by comparing the change between treatment groups using a mixed model with repeated measures (MMRM). The MMRM will compare the estimated change from baseline between treatments for the primary endpoint. This analysis will assess whether there is a difference in estimated CFB between active and placebo groups at 11 months.

The primary analysis of percent change from baseline to 11 months in MVO2 as measured by CPET will use the ITT methodology and an MMRM methodology with a random slope and intercept for each individual.

All secondary and exploratory endpoints CFB values will be analyzed using the MMRM Responder analyses will be run on MVO2 (primary), GST, T1MW, Peak Workload, mFARS, and CGI-C (functional assessment). The PK of D2-LA, D2-ARA, H2-LA, and H2-ARA will be characterized in terms of minimum and maximum exposure at steady state.

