8.3. Blinding

Subjects and study personnel, including but not limited to investigators, study coordinators, nursing staff, clinical monitors, the Sponsor, and the Sponsor's representatives, will remain blinded to the study treatment assignments (RT001 or placebo).

If there is a need to unblind the study drug assignment for a subject, the Principal Investigator will discuss with the sponsor's Medical Monitor. A separate unblinding plan will document the specific processes related to emergency unblinding. Refer to Section 15.7 for a description of emergency unblinding procedures.

The reason for unblinding must be documented in the source document for the subject. If a subject's study drug assignment is unblinded, the subject should remain in the study and continue the protocol-specified follow-up evaluations.

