9.3.3. Documentation of Withdrawal

The reason(s) for withdrawal from the study drug/study must be recorded in the subject's medical record and case report forms (CRF).

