9.3.4. Replacement of Subjects

Subjects who discontinue before enrollment is complete may be replaced in the study. Replacement subjects will be assigned unique subject numbers.

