13.12. Unscheduled Visits

Procedures to be performed at any unscheduled visit are at the discretion of the Investigator, but should at least include safety, laboratory, and health examinations necessary for collection of AE information. Any procedure can be repeated at an unscheduled visit as needed.

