13.13. Early Termination Visit

If the subject withdraws or is discontinued from the study the following safety procedures should be performed:

- Perform a complete physical examination
- Record vital sign measurements and weight
- Obtain a 12-lead ECG
- Obtain blood samples for hematology, chemistry, coagulation, and lipid profile
- Obtain a urinalysis sample (dipstick test, microscopic examination)
- Perform a urine pregnancy test for all female subjects unless there is documented evidence confirming they are not of childbearing potential

- Record AEs
- Record concomitant medications
- Perform drug accountability

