Change from baseline (CFB) will be analyzed by comparing the change between treatment groups using a mixed model with repeated measures (MMRM). The MMRM will compare the estimated change from baseline between treatments for the primary endpoint. This analysis will assess whether there is a difference in estimated CFB between active and placebo groups at 11 months.

The primary analysis will use the ITT methodology and an MMRM methodology with a random slope and intercept for each individual. Due to the small sample size the model will be optimized by implementation of two risk scores (baseline and slope) that account for multiple baseline covariates in one variable. The risk scores will be derived from blinded data using the GST change from baseline values and generated using the baseline model covariates (excluding treatment and visit; baseline risk score) or the baseline model covariates*time interactions (slope risk score). The risk scores will be included as covariates in the model.

To calculate the baseline risk score, the GST change score is regressed on the covariates listed below. Individual coefficients for the baseline risk score are multiplied by individual covariate values and summed. A separate slope risk score is calculated for baseline covariates interacting with time.

The MMRM with primary outcome CFB value as the response variable will include the following covariates and fixed effects:

- baseline risk score:
 - baseline score for GST
 - age
- slope risk score:
 - baseline score for GST * time
 - age*time
- Time (continuous)
- Time by treatment interaction (time*treatment)
- baseline score for parameter of interest (if not in GST)
- site pooled by region (random effect)

Model assumptions will be evaluated. If the parametric assumptions are evaluated as inappropriate or violated, rank analogues will be advanced.

All secondary and exploratory endpoints CFB values will be analyzed using the MMRM described above. This analysis will assess whether or not there is a difference in estimated CFB values between treatment group and placebo at the 11-month model estimate using least squares means estimates from the MMRM model.

Speech measurement reporting will be analyzed by a third party vendor. A separate report will be provided.

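### Nothing requires subjects who stop study drug to attend the later efficacy visits, so their Month 11 MVO2 can go uncollected in a primary analysis labelled ITT

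*Combined protocol and SAP*

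**What the plan says.** **Stopping and leaving.** Section 9.3.2: "If it is necessary for a subject to discontinue the study drug/study earlier than planned, subjects should complete Early Termination procedures". It also asks for the date of the last dose. For subjects who withdraw from the study, it provides phone follow-up to gather adverse event information. Section 9.3.3 uses the same joined term: "The reason(s) for withdrawal from the study drug/study must be recorded".

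**The Early Termination visit.** Section 13.13: "If the subject withdraws or is discontinued from the study the following safety procedures should be performed". The list covers physical examination, vital signs, ECG, laboratory tests, urinalysis, pregnancy test, adverse events, concomitant medication and drug accountability. CPET, T1MW and FARS-Neuro are absent.

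**Staying in follow-up.** Sections 8.3 and 15.7 say that after unblinding "the subject should remain in the study and continue the protocol-specified follow-up evaluations". No section says this for a subject who stops drug.

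**Analysis.** Section 14.1: "The primary analysis will use the ITT methodology and an MMRM methodology with a random slope and intercept for each individual". The synopsis likewise says that the primary analysis of "percent change from baseline to 11 months in MVO2 as measured by CPET will use the ITT methodology". Section 14.1 defines ITT as everyone randomized. The same section also says that efficacy analyses, the primary one included, address the on-treatment period and use the mITT and per-protocol populations unless something else is specified.

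**The concern.** An ITT comparison at Month 11 needs Month 11 outcomes from everyone randomized, including those who stopped the drug. A site that follows Section 9.3.2 can reasonably bring a drug stopper in for Early Termination, carry out the safety list and regard the subject as finished. MVO2 comes only from CPET, so no further primary outcome would exist for that subject. The first CPET on treatment is at Day 120 (Table 1), so someone who stops before then could contribute no post-baseline MVO2 at all.

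For these subjects the primary result would rest on a missing-at-random assumption that the trial's own data cannot test. A later SAP can choose how to handle missing values, but it cannot recover tests that were never done. The two population statements in Section 14.1 add a second difficulty: even where an off-drug value is collected, the plan gives conflicting signals on whether it counts.

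**Working it through.** **1. The texts side by side**

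| Question | 9.3.2 and 9.3.3 | 13.13 | 8.3 and 15.7 |
|---|---|---|---|
| Trigger | stopping drug or study, one joined term | leaving the study | unblinding |
| What follows | Early Termination procedures; reasons recorded under the joined term | safety procedures, no CPET or T1MW | subject stays and continues evaluations |

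A subject who stops drug but is willing to stay is sent to Early Termination by 9.3.2 and is not covered by the trigger in 13.13. The rule that would settle the matter is written only for unblinding.

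**2. The plan's own figure**

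Section 14.2 gives over 99% power for 30 per arm, a difference of 15.8 and an SD of 11.1 at two-sided 0.05. The noncentrality is 15.8 / (11.1 × √(2/30)) = 5.51 on 58 degrees of freedom, and the power is 0.9997, so the figure reproduces. With 40% of values lost in each arm (18 per arm), power is still 98.6%. The figure is for peak workload, not MVO2, so it does not transfer directly. On these inputs, though, the issue is bias and the meaning of the estimate, not power.

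**3. Withdrawal figures in the documents**

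None is given for this trial. Section 6.4 reports an earlier 28-day study in which 2 of 13 RT001 subjects (15.4%) and 0 of 6 comparator subjects withdrew.

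**4. Illustration on assumptions alone**

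Let D be the Month 11 difference under full adherence, built up on a straight line from baseline. A share p of active subjects stops after month s and loses a fraction f of the slope difference from then on. Stopping is unrelated to earlier outcomes.

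- Month 11 difference for a stopper: D × (1 − f × (11 − s)/11)
- ITT difference: D × (1 − p × f × (11 − s)/11)
- Target of a missing-at-random model without the off-drug values: D
- Relative overstatement: 1/(1 − p × f × (11 − s)/11) − 1

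D cancels, so the percentages do not depend on the plan's means or SD.

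| s | f | p = 5% | p = 10% | p = 20% |
|---|---|---|---|---|
| 4 | 1 | 3.3% | 6.8% | 14.6% |
| 4 | 0.5 | 1.6% | 3.3% | 6.8% |
| 8 | 1 | 1.4% | 2.8% | 5.8% |
| 8 | 0.5 | 0.7% | 1.4% | 2.8% |

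Largest cell: 0.20 × 1 × 7/11 = 0.1273, and 1/(1 − 0.1273) − 1 = 14.6%. Smallest cell: 0.05 × 0.5 × 3/11 = 0.0068, and 1/(1 − 0.0068) − 1 = 0.7%. With f = 0 the overstatement is zero. If placebo subjects who stop then do worse than the model predicts, the error runs the other way.

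**The case against.** The best defence is that nothing ends follow-up for a drug stopper. Section 13.13 speaks only of leaving the study, the slash in 9.3.2 can be read as and/or, and Section 13.12 says "Any procedure can be repeated at an unscheduled visit as needed". A careful site could keep such a subject on the Table 1 visits. The date of last dose and the reasons are already recorded, and analysis detail is deferred to a separate SAP. The dose reductions in Sections 8.1 and 11.1 may also make stopping rare.

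Much of this stands. Continued visits are permitted, and the stopping rate may be small. But permission leaves practice to each site, and deferral covers only which values are analysed, not whether they are collected.

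Some stronger readings are tempting but unsupported:

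- **The whole protocol treats stopping drug as leaving.** Only 9.3.2 and 9.3.3 join the two. Section 13.13 refers to the study alone.
- **Drug stoppers may be replaced.** Section 9.3.4 says "Subjects who discontinue before enrollment is complete may be replaced in the study" and does not say what is discontinued, but Section 14.2 ties replacement to discontinuing from the study.
- **The effect would be overstated by 11 to 43%.** That is the limit s = 0, f = 1 in the formula for 10 to 30% stopping: 1/0.90 − 1 = 11% and 1/0.70 − 1 = 43%. It assumes that stoppers end with the placebo mean and that only those still on drug are compared. No document supports those inputs, and the repeated-measures model also uses values from before the stop.
- **The 2 of 13 gives the stopping rate.** It comes from a very small 28-day study under another regimen. It shows that one-sided withdrawal can occur, not how often.

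**Conclusion.** The concern holds as a gap in data collection and a contradiction in the text. Sections 9.3.2 and 13.13 disagree on whether stopping drug leads to Early Termination. No section requires Month 11 MVO2 from drug stoppers, and Section 14.1 leaves the status of off-drug values contradictory. These points can be read directly from the documents.

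The consequence is much less certain. The 0.7 to 14.6% range rests entirely on assumed stopping shares, stopping times, loss of effect and a linear course. It is neither an estimate nor a bound: stopping before Month 4 would give larger values in the same formula, no change in course gives zero, and other patterns reverse the sign. A reader might infer that the trial will overstate the drug's effect; the documents do not support that. The change is still advisable, because it is cheap before the data are collected and impossible afterwards.

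**What to change.** - **Sections 9.3.2 and 9.3.3:** separate stopping drug from leaving the study, and record a date and reason for each. The date of last dose is already asked for. Align 13.13 with the result.
- **Follow-up:** state that consenting subjects who stop drug stay in the study and attend the remaining efficacy visits in Table 1 through Day 330.
- **Section 14.1:** state that these off-drug values enter the primary ITT model. Reconcile the sentence on the on-treatment period and the mITT and per-protocol populations with the ITT statement, because the two would otherwise conflict openly.
- **Optional, for subjects leaving the study:** add CPET and T1MW to the 13.13 visit, only with consent and where the investigator judges it safe. Section 14.1 lists time as continuous but does not say whether it is the actual date or the nominal month, so state which. Such a test does not replace the Month 11 value.

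The cost is protocol wording, extra CRF fields, and follow-up effort and visit burden at visits already scheduled. No dosing or drug-stopping rule changes.

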9.3.3. Documentation of Withdrawal

The reason(s) for withdrawal from the study drug/study must be recorded in the subject's medical record and case report forms (CRF).

9.3.4. Replacement of Subjects

Subjects who discontinue before enrollment is complete may be replaced in the study. Replacement subjects will be assigned unique subject numbers.

9.3.5. Termination of Study by Sponsor

Although the Sponsor has every intention of completing the study, the Sponsor reserves the right to discontinue the study at any time for clinical or administrative reasons, or if required by the

FDA or other regulatory authorities. Both the Sponsor and the Medical Monitor will review the safety of RT001 throughout the study. The study may be halted at any time for safety concerns.

9.4. Pregnancy

Pregnant women are not eligible for inclusion in the study. Before enrolling women of childbearing potential (WOCBP) in this clinical trial, Investigators must advise WOCBP of the importance of avoiding pregnancy during trial participation and the potential risk factors for an unintentional pregnancy. WOCBP must agree to use a medically acceptable and effective barrier method of contraception (e.g., condom with spermicide, birth control pill) prior to study entry and for the duration of study participation to avoid pregnancy throughout the study and for a period of at least 30 days after all study procedures are completed. Male subjects must also agree to use an accepted method of contraception for the duration of the study and for a period of at least 30 days after all study procedures are completed. This should be covered during the informed consent process.

10. INVESTIGATIONAL PRODUCT

10.1. Identity of Investigational Product

The investigational product is RT001. RT001 is encapsulated 9-cis, 12-cis-11,11-D₂-linoleic acid ethyl ester, which is a site-specific (C11) di-deutero synthetic homologue of LA ethyl ester. Each capsule contains 960 mg of RT001. The placebo product is composed of encapsulated USP safflower oil. The placebo capsules are identical in appearance and size to the investigational drug product. The study drug and placebo are indistinguishable. Both are described as opaque brown oblong soft-gel capsules.

10.2. Packaging and Labeling of Clinical Supplies

RT001 and placebo are supplied as soft-gelatin (softgel) capsules. RT001 and placebo capsules are provided in identical glass bottles each containing 42 softgel capsules.

10.3. Storage of Clinical Supplies

Study drug should be stored by the study site in a controlled refrigerated temperature of 2 to 8°C (35.6 to 46.4 °F). If the temperature exceeds or falls below this range, please report it to the Sponsor as outlined in the Pharmacy Manual. Study drug should be refrigerated by the subject once dispensed from the site. Please refer to Pharmacy manual for further details.

10.4. Study Drug Dispensation

The study drug for the first 4 weeks of dosing will be dispensed at the study sites. Study drug for the subsequent dosing may be shipped directly to the subject or site from a drug depot or site, depending on the dispensing schedule.

10.5. Drug Accountability

Subjects will be asked to return the used and unused study bottles to the study site or send it back to the depot. It is the responsibility of the Investigator or his/her designee to maintain drug accountability at the clinical trial site and ensure that a current record of investigational product disposition is maintained. It is the responsibility of the Investigator or his/her designee to ensure that the investigational product is used only in accordance with the approved protocol. All records or logs must comply with applicable regulations and guidelines. The Sponsor will provide forms to facilitate accountability if the staff at the investigational site does not have an established system that meets these requirements.

11. STUDY DRUGS AND OTHER MEDICATIONS, SUPPLEMENTS

11.1. Study Drug Administration

Subjects will receive instructions on taking the study drug with meals. RT001 should be administered with food, preferably at mealtime. On clinic visit days all subjects will receive the morning dose of study drug in the clinic.

Subjects will self-administer orally 9 capsules daily for the first month with a meal: 3 capsules with breakfast, 3 capsules with lunch, and 3 capsules with dinner for the first month. After this initial period the dose will be reduced to 6 capsules daily with a meal: 3 capsules with breakfast, and 3 capsules with dinner for the remainder of the trial, while on study drug. If a subject is unable to tolerate study drug because of adverse events during the initial loading period, the dose may be reduced to six capsules daily (5.76 g total dose) given as 3 capsules with breakfast, and 3 capsules with dinner. If a subject is unable to tolerate study drug because of adverse events after the dose reduction to six capsules daily (5.76 g total dose), the dose may be spread over three meals (2 capsules at breakfast, 2 capsules with lunch, and 2 capsules with dinner). If the subject is still unable to tolerate study drug after spreading it over three meals, the total dose may be reduced by 1-2 capsules/day, preferably by reducing the dose for a meal from 2 to 1 capsule(s) as needed. After 2 weeks of taking a dose of less than 6 caps/day, the subject should try to increase the dose again to 6 capsules/day given as 2 capsules TID given with meals. If 6 caps/day is not tolerable, the subject can take the drug at the dose of less than 6 caps/day that was tolerable. The last dose of study drug (3 capsules) will be taken 4 weeks from the Day 330 visit.

11.2. Prior and Concomitant Medications

Stable, ongoing therapies will be permitted during this study. Any drug therapy initiated during the study should be discussed with the Medical Monitor prior to administration, if possible. Data on concomitant medications will be collected at each visit.

Fish oils or other oil-based supplements should not be taken for the duration of the study. In addition, if subjects have participated in prior therapeutic trials, they will need to have been off therapy for at least 30 days prior to receiving the first dose of study drug. Changes in herbal remedies and changes in prescription medications are strongly discouraged during the trial.

11.3. Subject Compliance

Compliance will be assessed through counting the number of bottles/capsules returned to the investigational site by the subject. The site will contact the subject to confirm date of last study dose as well as to perform final drug accountability during the EOT call. The subject will be given instructions on how to return any unused study drug/bottles to the site.

